10.8.2 B-cell Phenotyping (Part B)

Antigen-specific B cells induced by vaccination will be identified and characterized using fluorescently-labeled recombinant proteins in combination with a flow cytometry phenotyping panel. In particular, HIV Env-reactive B cells will be enumerated and may be further characterized for expression of memory, activation, inhibitory or other markers by protein and/or gene expression. Antigen-specific B cells may also be sorted for further analysis by B cell receptor sequencing or gene expression analysis. Lastly, functional properties may be confirmed by cloning of the B cell receptor (VH and VL) genes into an IgG expression vector in order to express the antibody for functional characterization using binding, neutralization or other assay.

10.8.3 Tfh phenotyping

Flow cytometry may be used to identify peripheral blood follicular helper T (pTfh) cells. Phenotyping of pTfh cells will be based on expression of CXCR5 and PD-1 on CD4+ T cells, and may include additional markers. For example, if flow cytometry panels are successfully developed to assess CD69, OX40, IL-21

and CD154 expression as a functional read-out, vaccine-specific Tfh cells may be assessed and isolated for further analysis.

10.8.4 B cell plasmablasts

Flow cytometry may be used to identify the early precursors for antibody-secreting B cells, called B cell plasmablasts, in the peripheral blood. Plasmablasts will be mainly characterized by CD19+ CD20- and high expression of CD27 and CD38. The flow cytometry panels might also include additional markers and assessment of antigen specificity.

10.8.5 Mucosal studies (Part B)

Saliva, cervicovaginal fluid, rectal fluid, and semen samples will be collected at timepoints indicated in [Appendix I](#), then processed and assessed for HIV-specific IgA and IgG antibodies. Additional exploratory analyses may be performed on these samples.

10.8.6 Microbiome analysis

Swabs of stool will be shipped to a central laboratory. Specimens are processed to enable nucleic acid sequencing. 16s rRNA sequences will then be determined using sequencing approaches or other methods.

10.9 Specimen storage and other use of specimens

The HVTN stores specimens from all study participants indefinitely, unless a participant requests that specimens be destroyed or if required by IRB/EC, or RE.

Other use of specimens is defined as studies not covered by the protocol or the informed consent forms for the study (see [Appendix A](#) and [Appendix B](#)).

This research may relate to HIV, vaccines, the immune system, and other diseases. This could include genetic testing and, potentially, genome-wide studies. This research is done only to the extent authorized in each study site's informed consent form, or as otherwise authorized under applicable law. Other research on specimens ('other use') will occur only after review and approval by the HVTN, the IRB/EC of the researcher requesting the specimens, and the CRS's IRBs/ECs/REs if required.

As part of consenting for the study, participants document their initial decision to allow or not allow their specimens to be used in other research, and they may change their decision at any time. The participant's initial decision about other use of their specimens, and any later change to that decision, is recorded by their CRS in a Web-based tool that documents their current decisions for other use of their specimens. The HVTN will only allow other research to be done on specimens from participants who allow such use.

CRSs must notify HVTN Regulatory Affairs if institutional or local governmental requirements pose a conflict with or impose restrictions on specimen storage or other use of specimens.

10.10 Biohazard containment

As the transmission of HIV and other blood-borne pathogens can occur through contact with contaminated needles, blood, and blood products, appropriate precautions will be employed by all personnel in the drawing of blood and shipping and handling of all specimens for this study, as currently recommended by the CDC and the NIH or other applicable agencies.

All dangerous goods materials, including Biological Substances, Category A or Category B, must be transported according to instructions detailed in the International Air Transport Association Dangerous Goods Regulations.

11 Safety monitoring and safety review

11.1 Safety monitoring and oversight

11.1.1 HVTN 124 PSRT

The HVTN 124 PSRT is composed of the following members:

- DAIDS medical officer representative,
- Protocol chair and cochair,
- Protocol Team leader,
- Core medical monitor, and
- Clinical safety specialist.

The clinician members of HVTN 124 PSRT are responsible for decisions related to participant safety.

The Protocol Team clinic coordinator, clinical data manager, vaccine developer representative, clinical trial manager, and others may also be included in HVTN 124 PSRT meetings.

11.1.2 HVTN SMB

The SMB is a multidisciplinary group consisting of biostatisticians, clinicians, and experts in HIV vaccine research that, collectively, has experience in the conduct and monitoring of vaccine trials. Members of the SMB are not directly affiliated with the protocols under review.

The SMB reviews safety data, unblinded as to treatment arm, approximately every 4 months. The reviews consist of evaluation of cumulative reactogenicity events, AE, laboratory safety data, and individual reports of adverse events requiring expedited reporting to DAIDS. The SMB conducts additional special reviews at the request of the HVTN 124 PSRT.

Study sites will receive SMB summary minutes and are responsible for forwarding them to their IRB/EC and any applicable RE.

11.1.3 SDMC roles and responsibilities in safety monitoring

The roles and responsibilities of the SDMC in relation to safety monitoring include:

- Maintaining a central database management system for HVTN clinical data;

- Providing reports of clinical data to appropriate groups such as the HVTN 124 PSRT and HVTN SMB (see Section 11.1.2);

11.1.4 HVTN Core roles and responsibilities in safety monitoring

- Daily monitoring of clinical data for events that meet the safety pause and HVTN 124 PSRT AE review criteria (see Section 11.4);
- Notifying HVTN CRSs and other groups when safety pauses or planned holds are instituted and lifted (see Section 11.4);
- Querying HVTN CRSs for additional information regarding reported clinical data; and
- Providing support to the HVTN 124 PSRT.

11.2 Safety reporting

11.2.1 Submission of safety forms to SDMC

Sites must submit all safety forms (eg, reactogenicity, adverse experience, urinalysis, local lab results, and concomitant medications) before the end of the next business day after receiving the information. The forms should not be held in anticipation of additional information at a later date. If additional information is received at a later date, the forms should be updated and resubmitted before the end of the next business day after receiving the new information.

11.2.2 AE reporting

An AE is any untoward medical occurrence in a clinical investigation participant administered a study product/procedure(s) and which does not necessarily have a causal relationship with this treatment. An AE can therefore be any unfavorable and unintended sign (including an abnormal laboratory finding), symptom, or disease temporally associated with the use of an investigational study product/procedure(s), whether or not related to the investigational study product/procedure(s). All AEs are graded according to the Division of AIDS (DAIDS) Table for Grading the Severity of Adult and Pediatric Adverse Events, Corrected Version 2.1, July 2017, available on the RSC website at <http://rsc.tech-res.com/clinical-research-sites/safety-reporting/daids-grading-tables>, except:

- Unintentional weight loss is required to be reported as an AE only if it is considered to be potentially deleterious to the participant's health (see HVTN 124 Study Specific Procedures);
- Injection Site Erythema or Redness and Injection Site Induration or Swelling will not consider interference with usual social and functional activities such that:

- Grade 1 is: 2.5 to < 5 cm in diameter OR 6.25 to < 25 cm² surface area;
- Grade 2 is: ≥ 5 to < 10 cm in diameter OR ≥ 25 to < 100 cm² surface area;
- Grade 3 is: ≥ 10 cm in diameter OR ≥ 100 cm² surface area OR Ulceration OR Secondary infection OR Phlebitis OR Sterile abscess OR Drainage;
- Grade 4 is: Potentially life-threatening consequences (eg, abscess, exfoliative dermatitis, necrosis involving dermis or deeper tissue).

All AEs are reported to the SDMC on the appropriate CRF. Clinic staff should evaluate every AE to determine if (1) the AE meets the requirements for expedited reporting to DAIDS (see Section 11.2.3), and (2) if the AE meets the criteria for a safety pause/prompt AE review (see Section 11.4), and (3) if the AE is an AESI. A sample list of AESI is provided as [Appendix L](#).

Sites are expected to notify HVTN clinical safety staff of any serious safety concern requiring their attention (see [Table 11-1](#)). Telephone numbers and email addresses are found on the protocol home page on the HVTN Members' site (<https://members.hvtn.org/protocols/hvtn124>). Concerns requiring immediate attention should be communicated by calling the clinical safety phone.

In the case of email notification, the CSS will reply during working hours (local time) to confirm that the email has been received and reviewed. If email service is not available, the CRS should notify clinical safety staff of the event by telephone, then submit CRFs.

In addition, site investigators are required to submit AE information in accordance with IRB/EC and any applicable RE requirements.

11.2.3 Expedited reporting of adverse events to DAIDS

Requirements, definitions and methods for expedited reporting of AEs are outlined in Version 2.0 (January 2010) of the *Manual for Expedited Reporting of Adverse Events to DAIDS* (DAIDS EAE Manual), which is available on the RSC website at <http://rsc.tech-res.com/clinical-research-sites/safety-reporting/manual>. The SAE Reporting Category will be used for this study.

The internet-based DAIDS Adverse Experience Reporting System (DAERS) must be used for expedited AE (EAE) reporting to DAIDS. In the event of system outages or technical difficulties, expedited AE reports may be submitted via the DAIDS EAE Form. This form is available on the DAIDS RSC website at <http://rsc.tech-res.com/clinical-research-sites/safety-reporting/daids/paper-eae-reporting>.

For questions about DAERS, please contact [contact] or from within the DAERS application itself.

For questions about expedited AE reporting, please contact the DAIDS RSC Safety Office at [\([contact]\)](mailto:([contact])).

The study products for which expedited reporting are required are

- Env (A, B, C, A/E) / Gag (C) DNA plasmids or placebo
- Recombinant gp120 (A, B, C, A/E) proteins/GLA-SE adjuvant or placebo

In addition to the expedited Reporting Category identified above, any AE of vasculitis related to study product(s) must also be reported in an expedited manner.

While the participant is in the study reporting period (Section 3, Duration per participant), the SAE Reporting Category will be used.

After the protocol-defined AE reporting period for the study, unless otherwise noted, only Suspected, Unexpected Serious Adverse Reactions as defined in Version 2.0 of the DAIDS EAE Manual must be reported to DAIDS, if the study staff become aware of the events.

The NIAID/DAIDS will report all unexpected SAEs related to the study products observed in this clinical trial to the FDA in accordance with 21 CFR 312.32 (IND Safety Reports). However, because safety is a primary study endpoint, the Sponsor Medical Officer will not routinely be unblinded to study treatment assignment when there is an assessment of relatedness of the SAE with the study product(s); and the safety report will be sent to the FDA based on the blinded attribution assessment.

If the PSRT believes unblinding is appropriate (eg, if unblinding of the site PI to treatment assignment will assist with the clinical management of the SAE), the PSRT will consult the independent HVTN SMB for a recommendation. In the event the HVTN SMB determines that unblinding is indicated, the SMB will inform the individual (eg, site physician) of the participant's treatment assignment in such a manner as to maintain the study blind of the PSRT and study team. For additional impact and management of SAEs on the study, see Section 11.4.

11.3 Safety reviews

11.3.1 Initial safety evaluation

Enrollment across all participating HVTN CRSs will be restricted to a maximum of 1 participant per day until 6 participants have been enrolled in Group 1. The HVTN 124 PSRT will review the cumulative safety data including at minimum local and systemic reactogenicity data reported for the first 72 hours postvaccination on each of these 6 participants, and will determine whether it is safe to proceed with full enrollment in Group 1. The PSRT may consult with the HVTN SMB on an ad hoc basis for this evaluation.

11.3.2 Safety evaluation for moving from Part A to Part B

In addition to monitoring participant safety throughout the study period, the HVTN 124 PSRT will review all cumulative safety data available from Group 1, when data is available for the first 6 participants, up to and including the 2-week visit after the second vaccination, and from the second 6 participants, up to and including the 2-week visit after the first vaccination. Based on the assessment of this safety data, the PSRT will make a decision regarding the appropriateness of moving to Part B. The PSRT may consult with the HVTN SMB on an ad hoc basis for this evaluation.

11.3.3 Interim safety evaluation for Part B

Part B will first open to enrollment to 10 participants, randomized between Group 2 and Group 3. The PSRT will review all cumulative safety data available from the first 10 participants in Part B, up to and including the 2-week visit after the second vaccination, to make a decision regarding the appropriateness of proceeding with full enrollment in Part B. Based on the assessment of this safety data, the PSRT will make a decision regarding the appropriateness of proceeding with full enrollment in Part B. The PSRT may consult with the HVTN SMB on an ad hoc basis for this evaluation.

11.4 Safety pause and prompt PSRT AE review

When a trial is placed on safety pause, all enrollment and vaccination with the product related to the event that triggered the pause will be held until further notice. The AEs that will lead to a safety pause or prompt HVTN 124 PSRT AE review are summarized in [Table 11-1](#). Vaccinations may be suspended for safety concerns other than those described in the table, or before pause rules are met, if, in the judgment of the HVTN 124 PSRT, participant safety may be threatened. Criteria for an individual participant's departure from the schedule of vaccinations are listed in Section [7.3](#).

Table 11-1 AE notification and safety pause/AE review rules

Event and relationship to study products	Severity	HVTN CRS action ^a	HVTN Core action
SAE, related	Grade 5 or Grade 4	Phone immediately, email and submit forms immediately	Immediate pause
SAE, not related	Grade 5	Phone immediately, email and submit forms immediately	Immediate HVTN 124 PSRT notification
SAE, related	Grade 3	Email and submit forms immediately	Immediate HVTN 124 PSRT notification and prompt HVTN 124 PSRT AE review to consider pause
AE ^b , related	Grade 4 or 3	Email and submit forms immediately	Immediate HVTN 124 PSRT notification and prompt HVTN 124 PSRT AE review to consider pause
Vasculitis, related	Any grade	Phone immediately, email and submit forms immediately	Immediate pause
DTH responses, related	Any grade	Email and submit forms immediately	Prompt HVTN 124 PSRT notification and AE review to consider pause

^a Phone numbers and email addresses are found on the Protocol home page on the HVTN Members' site (<https://members.hvtn.org/protocols/hvtn124>).

^b Does not include subjective reactogenicity symptoms (injection site pain, tenderness, fatigue/malaise, myalgia, arthralgia, chills, headache, nausea).

For all safety pauses, HVTN Core notifies the HVTN 124 PSRT, HVTN Regulatory Affairs, DAIDS Pharmaceutical Affairs Branch (PAB), DAIDS Regulatory Affairs Branch (RAB), DAIDS Safety and Pharmacovigilance Team (SPT), and participating HVTN CRSs. When an immediate safety pause is triggered, HVTN Core notifies the SMB.

Once a trial is paused, the HVTN 124 PSRT reviews safety data and decides whether the pause can be lifted or permanent discontinuation of vaccination is appropriate, consulting the SMB if necessary. HVTN Core notifies the participating HVTN CRSs, HVTN Regulatory Affairs, DAIDS PAB, DAIDS RAB, and DAIDS SPT of the decision regarding resumption or discontinuation of study vaccinations. Based on the HVTN 124 PSRT assessment, DAIDS RAB notifies the FDA as needed.

If an immediate HVTN 124 PSRT notification or prompt HVTN 124 PSRT AE review is triggered, HVTN Core notifies the HVTN 124 PSRT as soon as possible during working hours (local time)—or, if the information was received during off hours, by the morning of the next workday. If a prompt HVTN 124 PSRT AE review cannot be completed within 72 hours of notification (excluding weekends and US federal holidays), an automatic safety pause occurs.

The HVTN requires that each CRS submit to its IRB/EC and any applicable RE protocol-related safety information (such as IND safety reports, notification of vaccine holds due to the pause rules, and notification of other unplanned safety pauses). CRSs must also follow all applicable RE reporting requirements.

In addition, all other AEs are reviewed routinely by the HVTN 124 PSRT (see Section 11.5.2).

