7.3 Participant departure from vaccination schedule or withdrawal

This section concerns an individual participant's departure from the vaccination schedule. Pause rules for the trial as a whole are described in Section [11.4](#).

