7.3.3 Discontinuing vaccination for a participant

Under certain circumstances, an individual participant's vaccinations will be permanently discontinued. Specific events that will result in stopping a participant's vaccination schedule include:

- Co-enrollment in a study with an investigational research agent (rare exceptions allowing for the continuation of vaccinations may be granted with the unanimous consent of the HVTN 124 PSRT).
- Clinically significant condition (ie, a condition that affects the immune system or for which continued vaccinations and/or blood draws may pose additional risk), including but not limited to the following:
 - Pregnancy (regardless of outcome)
 - Any grade 4 local or systemic reactogenicity symptom, lab abnormality, or AE that is subsequently considered to be related to vaccination
 - Vasculitis, regardless of grade or relatedness
 - Any grade 3 lab abnormality or other clinical AE (exception: fever or vomiting and subjective local and systemic symptoms) that is subsequently considered to be related to vaccination; upon review, the PSRT may allow continuation of vaccination if the event is grade 3 erythema and/or induration
 - Clinically significant type 1 hypersensitivity reaction associated with study vaccination. Consultation with the HVTN 124 PSRT is required

prior to subsequent vaccinations following any type 1 hypersensitivity reaction associated with study vaccination

- DTH reaction at previous study agent injection sites
- Investigator determination in consultation with Protocol Team leadership (eg, for repeated nonadherence to study staff instructions).
- Participant misses more than 2 vaccinations(s) (see Section [7.3.2](#)).

Such participants should be counseled on the importance of continuing with the study and strongly encouraged to participate in follow-up visits and protocol-related procedures per the protocol for the remainder of the trial, unless medically contraindicated.

In addition, vaccinations will be stopped for participants diagnosed with HIV infection. HIV-infected participants will not continue in the trial (see Sections [7.3.4](#) and [9.8.1](#)).

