9.11.1 Assessment of systemic and local symptoms

Systemic symptoms include increased body temperature, malaise and/or fatigue, myalgia, headache, chills, arthralgia, nausea, and vomiting. Local symptoms include pain and/or tenderness at the injection site. The daily maximum severity reached for each symptom during the assessment period is reported.

Body temperature is measured by oral or infrared thermometry and reported in degrees Celsius. If temperature is measured in Fahrenheit, the conversion to Celsius should be documented in the participant's chart note. A measurement is taken once daily during the assessment period and should be repeated if participant is feeling feverish.

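### Table 11-1, footnote b: a related, non-serious grade 4 subjective reaction triggers no mandatory PSRT notice and no review deadline

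*Protocol*

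**What the plan says.** Table 11-1 (Protocol Section 11.4) has six rows. The row for related adverse events that are not SAEs covers grades 3 and 4 together and requires immediate PSRT notification and a prompt PSRT review to consider a pause. Footnote b, attached to that row, reads: "Does not include subjective reactogenicity symptoms (injection site pain, tenderness, fatigue/malaise, myalgia, arthralgia, chills, headache, nausea". It mentions no grade.

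The text after the table attaches two time limits to such a trigger. HVTN Core must tell the PSRT during working hours, or on the morning of the following workday if the report came in off hours. If the prompt review is not finished within 72 hours of notification (weekends and federal holidays not counted), the trial pauses automatically. All other adverse events go to routine PSRT review, which Section 11.5.2 makes weekly during the injection phase.

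Section 7.3.3, on stopping an individual's vaccinations, separates the grades. At grade 4 there is no exception: "Any grade 4 local or systemic reactogenicity symptom, lab abnormality, or AE that is subsequently considered to be related to vaccination". At grade 3 there is one: "Any grade 3 lab abnormality or other clinical AE (exception: fever or vomiting and subjective local and systemic symptoms".

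Section 9.11.1 defines the solicited symptoms: "Systemic symptoms include increased body temperature, malaise and/or fatigue, myalgia, headache, chills, arthralgia, nausea, and vomiting", and "Local symptoms include pain and/or tenderness at the injection site".

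**The concern.** Exempting subjective symptoms at grade 3 is understandable: a prompt review for each severe sore arm or headache would burden the PSRT for little return. The same reasoning does not carry over to grade 4, which Section 7.3.3 treats as grounds for permanently ending a participant's vaccinations. Because footnote b does not distinguish the grades, the ordering is odd. A related grade 3 vomiting episode triggers prompt PSRT review, while a related, non-serious grade 4 headache that ends a participant's vaccinations does not.

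At stake is how soon the team that can pause the trial must hear of such a reaction. Section 4.8 says these vaccines have had no previous clinical study. There is reason to watch subjective symptoms. Section 4.8.1 reports high reactogenicity with the predecessor regimen, including muscle pain, fatigue, headache and joint pain. Section 4.8.2 reports fever and chills with 5 mcg GLA-SE in one earlier study, which is the dose used here, although it also calls that dose generally well tolerated. This makes the concern plausible but supplies no rate of grade 4 reactions.

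**Working it through.** No error rate or sample-size formula applies, and the plan gives no figure to reproduce. The check traces one event through the rules: a related, non-serious, grade 4 reaction from footnote b's list.

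**Step 1. Table 11-1, row by row.**

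| Row | Applies? | Reason |
|---|---|---|
| SAE, related, grade 5 or 4 | No | Event is not serious |
| SAE, not related, grade 5 | No | Not serious; related; not grade 5 |
| SAE, related, grade 3 | No | Not serious; not grade 3 |
| AE, related, grade 4 or 3 | No | Removed by footnote b |
| Vasculitis, related | No | Different event |
| DTH, related | No | Different event |

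Rows that apply: 0 of 6.

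**Step 2. Other rules that might force notice or a deadline.**

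- Section 11.2.1: safety forms, including reactogenicity forms, reach the data center by the end of the next business day. This moves the data but requires no one to alert the PSRT.
- Sections 11.1.4 and 11.5.1: Core's stated daily review covers expedited events and events meeting the pause or prompt-review criteria. An event outside the table and not expedited is outside that scope. Section 2.5 says more broadly that Core monitors safety daily, but it refers to Section 11 for the detail.
- Section 9.11: a reaction worse than mild is generally seen by a clinician within 48 hours. No PSRT step follows from this.
- Section 11.3: the enrollment gates include PSRT review of reactogenicity data. The last covers the first 10 Part B participants through two weeks after their second vaccination. No gate is scheduled after it, either for the third to fifth vaccinations or for the other 48 − 10 = 38 Part B participants.
- Section 11.5.2: weekly PSRT review during the injection phase. This is the default next required look.

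**Step 3. Share of solicited symptoms affected.** Count as footnote b does, with fatigue/malaise as one item and pain and tenderness as two.

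- Section 9.11.1: 8 systemic + 2 local = 10.
- Named in footnote b: 8.
- Left in the prompt-review row at grade 4: 10 − 8 = 2 (raised temperature and vomiting).
- Subject to individual stopping at related grade 4 under Section 7.3.3: 10 of 10.

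Counting pain and tenderness as one item gives 7 of 9. The count is of list items and does not measure risk. It leaves out erythema, induration, lesions and lymph nodes, which are assessed separately and which footnote b does not name.

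**Step 4. The two routes compared.**

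| | Inside the row | Excluded by footnote b |
|---|---|---|
| PSRT notified | By the following workday's morning at the latest | No required notice |
| PSRT review | Within 72 hours, or automatic pause | Weekly review, or an enrollment gate if sooner |

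**The case against.** The strongest objection is that the affected class may be nearly empty. The SAP's safety listings (Section 9.2) pair severe with life-threatening reactogenicity, which suggests that grade 4 means life-threatening, and Section 11.2.2 describes grade 4 erythema or induration in similar terms. Many related grade 4 reactions may therefore be SAEs, and those pause the trial at once, a stronger response than prompt review. This stands as a limit on size. It does not close the gap: Table 11-1 itself provides for related grade 4 events that are not SAEs, and neither the grading table nor the expedited-reporting manual is in the documents to show that the class is empty.

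Second, the two rule sets serve different purposes and need not match. Section 7.3 says so: "Pause rules for the trial as a whole are described in Section" 11.4. That is correct, and the mismatch is not an error in itself. It does show that the protocol separates grade 3 from grade 4 for these symptoms elsewhere.

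Third, other layers remain. Section 11.2.2 says: "Sites are expected to notify HVTN clinical safety staff of any serious safety concern requiring their attention". Section 11.4 adds: "Vaccinations may be suspended for safety concerns other than those described in the table, or before pause rules are met", where the PSRT judges that safety may be threatened. The affected participant is stopped, and early Group 1 enrollment is limited to one participant per day until six are enrolled, with a PSRT review of their 72-hour data. All of this stands. None of it requires PSRT notice of the individual event or sets a deadline for reviewing it.

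**Conclusion.** The point holds. As written, footnote b leaves a related, non-serious grade 4 subjective reaction without mandatory immediate PSRT notification and without the 72-hour review limit. The practical difference is notice by the following workday against a wait of up to about a week for the routine review, unless site judgment or an enrollment gate brings it forward.

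It is a minor, optional improvement to a design choice. Such reactions do not go unreviewed, and the participant is not vaccinated again once the reaction is judged related. No number of events, doses or days saved can be given. The conclusion rests on the wording of the rules, and its practical reach depends on how many grade 4 subjective reactions would not be SAEs, which the documents do not show.

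**What to change.** In footnote b of Table 11-1, insert the words *grade 3* before *subjective*, so that the exclusion applies at that grade only. Related grade 4 subjective reactions then fall into the existing row, and the daily screens in Sections 11.1.4 and 11.5.1 cover them without further edits. Common grade 3 symptoms stay exempt, and Section 7.3.3 needs no change.

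The cost is two words in one footnote and no new data collection. The downside is some additional prompt PSRT reviews, each carrying an automatic pause if it runs past 72 hours. Without a rate in the documents their number cannot be bounded, but it would be small if the class is as small as the main objection supposes.
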